12.6.2. Collection of Pregnancy Information

- Investigator will collect pregnancy information on any female subject, who becomes pregnant while participating in this study
- Information will be recorded on the appropriate form and submitted to GSK within 2 weeks of learning of a subject's pregnancy.
- Subject will be followed to determine the outcome of the pregnancy. The investigator will collect follow up information on mother and infant, which will be forwarded to GSK. Generally, follow-up will not be required for longer than 6 to 8 weeks beyond the estimated delivery date.
- Any termination of pregnancy will be reported, regardless of fetal status (presence or absence of anomalies) or indication for procedure.
- While pregnancy itself is not considered to be an AE or SAE, any pregnancy complication or elective termination of a pregnancy will be reported as an AE or SAE.
- A spontaneous abortion is always considered to be an SAE and will be reported as such.
- Any SAE occurring as a result of a post-study pregnancy which is considered reasonably related to the study treatment by the investigator, will be reported to GSK as described in [Appendix 4](#). While the investigator is not obligated to actively seek this information in former study participants, he or she may learn of an SAE through spontaneous reporting.

Any female subject who becomes pregnant while participating

- will discontinue study medication or be withdrawn from the study]
- Investigator will attempt to collect pregnancy information on any female partner of a male study subject who becomes pregnant while participating in this study. This applies only to subjects who are randomized to receive study medication.

- After obtaining the necessary signed informed consent from the female partner directly, the investigator will record pregnancy information on the appropriate form and submit it to GSK within 2 weeks of learning of the partner's pregnancy
- Partner will also be followed to determine the outcome of the pregnancy. Information on the status of the mother and child will be forwarded to GSK.
- Generally, follow-up will be no longer than 6 to 8 weeks following the estimated delivery date. Any termination of the pregnancy will be reported regardless of fetal status (presence or absence of anomalies) or indication for procedure.

12.7. Appendix 7: Patient Reported Outcomes Questionnaires

12.7.1. FluPro

CCI - This section contained Clinical Outcome Assessment data collection questionnaires or indices, which are protected by third party copyright laws and therefore have been excluded.

Monday, August 27, 2012, FLU-PRO Version 1.0

Research Tool in Development: Do NOT copy or distribute

12.7.2. Katz ADL Score

CCI - This section contained Clinical Outcome Assessment data collection questionnaires or indices, which are protected by third party copyright laws and therefore have been excluded.

12.8. Appendix 8 - Country Specific Requirements

French subjects: In France, a subject will be eligible for inclusion in this study only if either affiliated to or a beneficiary of a social security category.

12.9. Appendix 9 Statistical considerations

12.9.1. Introduction

This document describes the adaptive design for study 201023 for danirixin (DNX; GSK1325756) in hospitalized influenza subjects. The purpose of this document is to provide an overview of the trial design and simulation results. Simulations were performed using Dose finding module in FACTS version 4.0.

The trial design is based on the primary efficacy endpoint of time to clinical response. The goal of the trial is to assess the efficacy of DNX and to identify whether there is a dose with acceptable efficacy based on TTCR. An adaptive design is proposed that allows for dropping an in-effective dose, stopping the study for futility and/or stopping the study for early success.

The trial will enroll up to a maximum of approximately 300 subjects over the course of 3 flu seasons. Interim analyses will be conducted after each season with approximately 75 to 100 subjects. At each interim analysis, the predictive probability of success based on TTCR will be calculated and used to support go/no-go decisions.

12.9.2. Statistical Modeling

At each interim analysis and at the final analysis, the TTCR data will be analyzed with independent dose-response models. The adaptation will be based on the predictive probability of success.

12.9.2.1. Hazard Model:

Let T_0 be the time to clinical response for the control arm with exponential distribution

$$T_0 \sim \text{Exp}(\lambda)$$

Where λ is the hazard rate constant of subjects in the control arm, the parameter is modeled as:

$$\lambda \sim \text{Gamma}\left(n, \frac{n}{\mu}\right)$$

Where n is prior weight parameter and μ is prior mean parameter, we set $n=4$ and $\mu=0.83$ based on the hazard rate observed in study NAI114373.

And T_d be the time to clinical response for the dose level d :

$$T_d \sim \text{Exp}(h_d)$$

where $h_d = \lambda e^{\theta_d}$, and θ_d is log-hazard ratio.

12.9.2.2. The dose –response Model:

Independent dose-response model estimate the response for each arm separately with normal distribution.

$$\theta_d \sim N(\mu_d, \nu_d^2)$$

Where θ_d is log-hazard ratio compared to control arm on the treatment arm d . The two dose levels considered are $d=1$ (15 mg BID), and $d=2$ (50 mg BID). μ_d is the mean of dose d and ν_d^2 is the variance of dose d . The same non-informative prior $N(0,1)$ is used for all doses of the dose-response model.

12.9.3. Allocation

The allocation ratio is 1:2:2 for the control arm, DNX 15 mg (dose level 1) and DNX 50 mg (dose level 2), respectively. If an arm is dropped after interim analysis, allocation will be kept the same for the remaining arms and the study size will be decreased.

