4.1.2. Safety Review Prior to Enrollment of Subjects with Severe Conditions at Baseline

The enrollment of critically ill hospitalized subjects will be delayed until IDMC review of the safety data from approximately 30 subjects considered to be less severe (Section 4.3).

The available safety data from subjects in this less severe population will be reviewed by the IDMC (unblinded) and GSK Safety Review Team (SRT) (blinded) after completion of study treatment. Enrollment of critically ill subjects (with normal renal function, and those with mild or moderate renal impairment) will only begin after an acceptable outcome is reported from the IDMC review of approximately 30 less severe subjects with normal renal function.

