4.1.3. Study Design Change in the Event of Widespread OSV Resistance

A contingency study design is included in this protocol to facilitate rapid implementation of a global design change should widespread resistance to OSV occur during the course of the study.

If pre-defined criteria for widespread OSV resistance are met, OSV will be temporarily or permanently discontinued. Antivirals that are recommended at the time of OSV resistance will be provided as open-label treatment, and enrollment in the study will continue. The criteria for implementation of this study design change are:

- Evidence of substantial OSV resistance in circulating influenza viruses in participating countries in the relevant geographic areas reported by World Health Organization (WHO) or Centers for Disease Control (CDC), defined as $\geq 20\%$ resistance in total of all circulating strains (e.g. $\geq 50\%$ resistance in Pandemic Influenza A (H1N1) viruses which constitutes $\geq 20\%$ of circulating strains), **OR**
- WHO or CDC recommend against treatment with single agent OSV.

In the absence of recommendations from WHO or CDC, other national health agencies in participating countries may recommend against treatment with single agent OSV for influenza treatment based on resistance patterns within a specific geographical area or country, or medical consensus. In these situations, a decision on whether to put enrollment on temporary hold at impacted site(s) should be made by investigators in consultation with local institutional review boards or ethics committees (IRB/IECs) and regulatory authorities.

While rapid diagnostic tests are not widely available to determine influenza strain or resistance, some study sites will have access to local laboratories with these capabilities that could allow appropriate subjects to continue to be enrolled.

[figure not shown]
The OSV arm may be re-instated if the level of OSV resistance diminishes below the criteria defined in the protocol, and if it is appropriate to do so, based on predicted patterns of circulating influenza strains.

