9.4. Key Elements of Analysis Plan

9.4.1. Efficacy

9.4.1.1. Primary Analysis

Probability of success, denoted Prob(Success), will be calculated. Success is defined as a statistically significant treatment effect (p-value<0.025 for hazard ratio of TTCR >1) in a future two-arm comparative superiority study with 300 subjects per arm, given observed data.

Let T_0 be the time to clinical response for the control arm with exponential distribution

$$T_0 \sim \text{Exp}(\lambda)$$

Where λ is the hazard rate constant of subjects in the control arm, the parameter is modeled as:

$$\lambda \sim \text{Gamma}\left(n, \frac{n}{\mu}\right)$$

Where n is prior weight parameter and μ is prior mean parameter, we set n=4 and $\mu=0.83$ based on the hazard rate observed in study NAI114373.

Let T_d be the time to clinical response for the dose level d :

$$T_d \sim \text{Exp}(h_d)$$

where $h_d = \lambda e^{\theta_d}$, and θ_d is log-hazard ratio and modeled with independent dose-dose response model.

Kaplan-Meier estimates for the median of TTCR for each treatment group and the median difference and 95% confidence interval (CI) between DNX arms and OSV will be provided.

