12.9.11. Operating Characteristics

[figure not shown]
[Table 12](#) shows the operating characteristics for different scenarios by interim analysis and final analysis. [Figure 1](#) and [Figure 2](#) show the possible sample size, corresponding probability of the sample size and cumulative probability of sample size under two selected scenarios.

Table 12 Operating Characteristics by Interim of Selected Scenarios

Scenario	Hazard ratio	Interim 1 n=100				Interim 2 n=200				Final	Average Sample size
		P(drop low dose)	P(drop high dose)	P(stop study for futility) (Observed HR 0.85 – 1.2)	P(stop study for efficacy) (Observed HR 1.5 – 3.2)	P(drop low dose)	P(drop high dose)	P(stop study for futility) (Observed HR 1 – 1.15)	P(stop study for efficacy) (Observed HR 1.55 – 2.7)		
1. No effect	L: HR=1 H: HR=1	15%	19%	46%	1%	2%	3%	25%	0%	9%	160
2. Small effect	L: HR=1.2 H: HR=1.2	16%	15%	22%	5%	4%	5%	10%	3%	45%	208
3. Large effect	L: HR=1.5 H: HR=1.5	7%	8%	4%	26%	1%	1%	2%	19%	90%	208
4. Mixed effect	L: HR=1.2 H: HR=1.5	31%	2%	8%	18%	8%	0%	3%	13%	82%	207
5. High dose large effect	L: HR=1 H: HR=1.5	54%	1%	10%	18%	12%	0%	3%	12%	81%	191

Futility rule at Interim: Drop dose: Prob(success) for the dose < 30%, Stop study for futility: Prob(success) for best dose< 30%, Stop study for efficacy: Prob(success) for best dose> 90%; Final success criteria: Prob(success) for best dose>50%
Success is defined one side $p \leq 0.025$ in a two arm superiority study with $n=300$ per arm.

Figure 4 Sample Size Distribution for an effective drug and an ineffective drug

Location of brown line on x-axis shows possible study sample size, height of brown line shows probability of the sample size, and blue line shows the cumulative probability of study sample size. Top panel shows an example of an ineffective drug with HR =1 for both doses; the bottom panel shows an example of an effective drug with HR =1.2 for low dose and HR=1.5 for high dose.

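### Protocol design: the final contrast for a dose dropped at an interim partly uses placebo subjects randomised after that dose closed, so any shared drift across seasons biases it

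*Protocol*

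**What the plan says.** Protocol 12.9.1: "The trial will enroll up to a maximum of approximately 300 subjects over the course of 3 flu seasons". Section 12.9.3 sets the allocation: "The allocation ratio is 1:2:2 for the control arm, DNX 15 mg (dose level 1) and DNX 50 mg (dose level 2), respectively". It then covers a dropped arm: "If an arm is dropped after interim analysis, allocation will be kept the same for the remaining arms and the study size will be decreased". Placebo and the surviving dose therefore continue at 1:2.

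The model in 9.4.1.1 and 12.9.2.1 has one control parameter λ, which "is the hazard rate constant of subjects in the control arm, the parameter is modeled as" a Gamma distribution. Each dose has hazard λ·exp(θ_d). There is no season index, stratum or covariate. Section 12.9.2 applies the model at every interim and at the final analysis. Season is not among the minimisation factors in 6.2.

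For reporting, 9.4.1.1 promises that "the median difference and 95% confidence interval (CI) between DNX arms and OSV will be provided", with no limit on which placebo subjects are used. The Table 12 footnote in 12.9.11 reads "Final success criteria: Prob(success) for best dose>50" per cent. Neither that footnote nor 12.9.7–12.9.9 says whether a dropped dose can be the best dose.

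Two planned features could shift recovery over time. Section 4.1.2: "The enrollment of critically ill hospitalized subjects will be delayed until IDMC review of the safety data from approximately 30 subjects". Section 4.1.3, if oseltamivir resistance becomes widespread: "Antivirals that are recommended at the time of OSV resistance will be provided as open-label treatment, and enrollment in the study will continue".

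The SAP (2.1, 3.1, 7.1.2) records termination after 10 subjects, with no formal interim, no model and descriptive summaries only.

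**The concern.** While all three arms are open, fixed allocation keeps them balanced within each season, so a pooled control does no harm. Once a dose closes at the first interim, it has season 1 subjects only, while λ and the placebo Kaplan-Meier curve take in all seasons. The comparison then mixes the dose effect with any change in recovery between seasons.

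Dropping a dose is not rare in the plan's own simulations. Table 12 drops the low dose at interim 1 in 31% of trials in the mixed-effect scenario and 54% in scenario 5. Under no effect, 15% drop the low dose and 19% the high dose at that interim.

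At stake are the reported effect of a dropped dose, any dose-response reading that uses it, and possibly the success decision.

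**Working it through.** **Inputs.** 20 placebo, 40 low-dose and 40 high-dose subjects per season (6.2, Table 2); medians 5.8 days (less severe) and 20.1 days (critically ill) from Table 8; follow-up to day 45 (4.2); priors Gamma(4, 4/0.83) on λ and N(0,1) on each θ_d; cut-offs 0.3, 0.9 and 0.5 (12.9.6–12.9.9). The share of critically ill subjects and any seasonal change in hazard are **assumptions**; the documents give neither.

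**1. The plan's own figures.** The protocol states 9% type I error at HR 1/1 and 82% power at HR 1.2/1.5. Simulating the rules with 300 per arm in the future trial (about 600 events) gives 18.7% and 90.7%. With about 300 future events in total the results are 8.8% and 82.4%, and average N at HR 1/1 is 159 against the stated 160. Not all simulation settings are given, so this does not show the stated figures to be wrong. The simulations below use 300 total events because that setting matches Table 12.

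**2. Closed-form bias for a null dose dropped at interim 1.** For daily hazard h with censoring at day 45, expected events per subject are e = 1 − exp(−45h) and person-time is p = e/h.

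- Less severe: h = ln 2/5.8 = 0.1195, e = 0.9954, p = 8.329 days.
- Critically ill: h = ln 2/20.1 = 0.0345, e = 0.7881, p = 22.855 days.
- With critically ill share q: e(q) = (1 − q)·0.9954 + q·0.7881 and p(q) = (1 − q)·8.329 + q·22.855.
- Apparent HR = [e₁/p₁] ÷ [(e₁ + 2e₂)/(p₁ + 2p₂)], where subscript 1 is season 1 and 2 is each later season.

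*Only about the first 30 of 100 season 1 subjects restricted* (4.1.1, 4.1.2; season 1 share 0.7q). At q = 0.5:

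- dose rate 0.9228/13.413 = 0.0688;
- placebo rate (0.9228 + 2 × 0.8918)/(13.413 + 2 × 15.592) = 0.0607;
- HR 1.13.

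*No critically ill subjects in season 1.* At q = 0.5:

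- dose rate 0.9954/8.329 = 0.1195;
- placebo rate (0.9954 + 2 × 0.8918)/(8.329 + 2 × 15.592) = 0.0703;
- HR 1.70.

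| Later-season share q | First 30 restricted | None in season 1 |
|---|---|---|
| 10% | 1.04 | 1.13 |
| 20% | 1.07 | 1.27 |
| 30% | 1.09 | 1.41 |
| 50% | 1.13 | 1.70 |

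If instead the whole season 2–3 hazard is 0.8, 0.67 or 0.5 of season 1, the HR is 1.17, 1.33 or 1.65. With concurrent placebo it is 1.00 in every case.

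A later drop does less harm. With recovery 10, 20 or 30% slower each season, the HR is 1.12, 1.27 or 1.49 for a drop at interim 1 and 1.06, 1.13 or 1.23 at interim 2.

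**3. Simulation (both doses HR 1).** Simulated HRs run a little lower, because doses are dropped for poor early results.

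- Later hazard 0.8, 0.67 or 0.5: pooled HR about 1.1, 1.3 and 1.6; with concurrent placebo about 0.95.
- First 30 restricted, q from 10 to 50%: pooled HR about 0.96–1.09. If re-scored, the dropped dose would meet the success rule in roughly 3–13% of trials that drop one. Overall type I error is 10–11% counting any dose and 9–10% counting open doses only.
- Larger drifts, any dose against open doses only: 13.2% v 5.5% (later hazard 0.5); 13.0% v 8.1% (none in season 1, 30% later); 14.8% v 6.3% (none in season 1, 50% later). With no drift it is 8.9% v 8.0%.

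**4. Retained doses.** A dose that stays open is 2:1 with placebo in every season, so drift does not confound it.

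**The case against.** The strongest reply is that nothing in the documents shows drift of a size that matters. Section 4.1.2 holds critically ill subjects back only until about 30 less severe subjects have been reviewed. Section 4.1.1 then admits both groups, and season 1 targets about 100 (4.1). A season 1 with no critically ill subjects is therefore not what the plan describes, though a slow review would move towards it. This stands, and it makes the small figures the better guide for severity mix. The hazard multipliers are also assumed. The antiviral switch is a contingency with no stated direction of effect, and faster later seasons would bias the dropped dose downward.

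A reader might infer that the protocol would declare a dropped dose successful and so inflate its stated 9%. The text does not support that: no sentence says a closed arm is re-scored or remains eligible as best dose. Section 12.9.4 also brings safety, biomarker and other efficacy data into stopping decisions.

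The severity subgroup in 9.4.1.3 gives partial protection, since Kaplan-Meier estimates are repeated within severity. It does not reach Prob(success) or drift from other causes.

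Finally, pooling is not stated in words. It follows from the single λ and the absence of any concurrent-control rule.

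**Conclusion.** The point holds as a cheap improvement to the protocol design. Followed as written, the final contrast for a dropped dose uses non-concurrent placebo and is biased by any shared drift, in a direction that depends on the drift.

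The size is uncertain. Under the entry restriction the protocol describes, the spurious HR for a null dose is about 1.0–1.1, with overall type I error essentially unchanged. It reaches about 1.1–1.7 only under assumed conditions: no critically ill subjects in season 1 and 10–50% later, or a later hazard of 0.5–0.8 of season 1. Type I error of 13–15% needs the larger of those drifts and also a rule, absent from the protocol, that a dropped dose can still be best dose. It should not be quoted as a property of the design. The simulated figures rest on about 300 future events in total.

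No result of this study is affected, because the SAP has no interim and no model.

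**What to change.** In 9.4.1.1 and 12.9.2–12.9.9 of the protocol design, add two sentences:

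1. Each dose is compared, for the hazard ratio, Prob(success) and the Kaplan-Meier median difference, only with placebo subjects randomised while that dose was open.
2. Prob_max(success) at later interims and at the final analysis is taken over the doses still open.

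Retained doses keep all their placebo subjects. The costs are a re-run of the simulations and a wider interval for a dropped dose: about 20 placebo subjects instead of up to 60 if it closes at interim 1. A separate control hazard per season is not proposed, because it would require re-specifying the Gamma prior and would change the analysis of retained doses. Since the study has ended, the change matters only if the design is used again.

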12.9.4. Evaluation of Arm Dropping, Trial Success and Futility

There will be one interim analysis after each season, with expectation that approximately 75-100 subjects will enroll in each season. Overall safety, biomarker and other efficacy data will be used for the decision of stopping the trial for futility and success. Early futility and success rules described below rely on the efficacy result based on TTCR.

12.9.5. Probability of success

Probability of success, denoted $\text{Prob}(\text{Success})$, will be used to evaluate futility, arm dropping and early success. Success is defined as a statistically significant treatment effect ($p\text{-value} < 0.025$ for hazard ratio of $\text{TTCR} > 1$) in a two-arm comparative superiority study with 300 subjects per arm, given observed data at interim and final analyses.

12.9.6. Arm Dropping

An ineffective DNX arm will be dropped if:

1. At least 75 subjects must have been enrolled.
2. Probability of success of the arm is less than 30%.
 $\text{Prob}_d(\text{success}) < 0.3$

12.9.7. Early Futility

To stop early for futility two conditions are required:

1. At least 75 subjects must have been enrolled.
2. Probability of success of the best dose, denoted as $\text{Prob}_{\max}(\text{success})$, is less than 30%.

$$\text{Prob}_{\max}(\text{success}) < 0.3$$

12.9.8. Early success

To stop early for success two conditions are required:

1. At least 75 subjects must have been enrolled.
2. Probability of success of the best dose, denoted as $\text{Prob}_{\max}(\text{success})$, is greater than 90%.

$$\text{Prob}_{\max}(\text{success}) > 0.9$$

12.9.9. Trial completion

The final analysis will occur when both accrual and follow-up are complete for all subjects. If at the completion of the trial, $\text{Prob}_{\max}(\text{success})$ is at least 50% , there is evidence of efficacy with regard to TTCR.

$$\text{Prob}_{\max}(\text{success}) > 0.5$$

12.9.10. Simulation Scenarios

In order to characterize and understand the performance of the design, we simulated the trial under several different scenarios.

Scenarios considered for the true hazard ratios for low dose and high dose DNX are shown in [Table 11](#).

Table 11 Dose- Response profile for Hazard Ratio

	DNX 15mg + OSV	DNX 50mg + OSV
1. No effect	1	1
2. Small effect	1.2	1.2
3. Large effect	1.5	1.5
4. Mixed effect	1.2	1.5
5. High dose large effect	1	1.5

12.9.11. Operating Characteristics

[figure not shown]
[Table 12](#) shows the operating characteristics for different scenarios by interim analysis and final analysis. [Figure 1](#) and [Figure 2](#) show the possible sample size, corresponding probability of the sample size and cumulative probability of sample size under two selected scenarios.

Table 12 Operating Characteristics by Interim of Selected Scenarios

Scenario	Hazard ratio	Interim 1 n=100				Interim 2 n=200				Final	Average Sample size
		P(drop low dose)	P(drop high dose)	P(stop study for futility) (Observed HR 0.85 – 1.2)	P(stop study for efficacy) (Observed HR 1.5 – 3.2)	P(drop low dose)	P(drop high dose)	P(stop study for futility) (Observed HR 1 – 1.15)	P(stop study for efficacy) (Observed HR 1.55 – 2.7)		
1. No effect	L: HR=1 H: HR=1	15%	19%	46%	1%	2%	3%	25%	0%	9%	160
2. Small effect	L: HR=1.2 H: HR=1.2	16%	15%	22%	5%	4%	5%	10%	3%	45%	208
3. Large effect	L: HR=1.5 H: HR=1.5	7%	8%	4%	26%	1%	1%	2%	19%	90%	208
4. Mixed effect	L: HR=1.2 H: HR=1.5	31%	2%	8%	18%	8%	0%	3%	13%	82%	207
5. High dose large effect	L: HR=1 H: HR=1.5	54%	1%	10%	18%	12%	0%	3%	12%	81%	191

Futility rule at Interim: Drop dose: Prob(success) for the dose < 30%, Stop study for futility: Prob(success) for best dose< 30%, Stop study for efficacy: Prob(success) for best dose> 90%; Final success criteria: Prob(success) for best dose>50%
Success is defined one side $p \leq 0.025$ in a two arm superiority study with $n=300$ per arm.

Figure 4 Sample Size Distribution for an effective drug and an ineffective drug

Location of brown line on x-axis shows possible study sample size, height of brown line shows probability of the sample size, and blue line shows the cumulative probability of study sample size. Top panel shows an example of an ineffective drug with HR =1 for both doses; the bottom panel shows an example of an effective drug with HR =1.2 for low dose and HR=1.5 for high dose.
